Itch Diary Review/compliance			X	X	X	X	X
Skin biopsy		X				X	
Plasma/PBMC isolation from blood draw		X				X	X
Labs from Blood Draw (CMP, CBC, Lipid panel, IgE)	X	X	X	X	X	X	
Patient who are HBcAB-positive and HBV DNA-negative at baseline require HBV DNA monitoring		X	X			X	

Approval Date: 3/16/2022
Principal Investigator: [name]
Application Number: IRB00262268

b. If your study involves data/biospecimens from participants enrolled under other research studies with a written consent or under a waiver of consent, please list the IRB application numbers for those studies. Please note: Certificate of Confidentiality (CoC) protections applied to the data in source studies funded by NIH or CDC will extend to this new study if the funding was active in 2016. If this situation applies, Section 36, question 6 in the application will need to be answered "Yes" and "Hopkins Faculty" should be selected in question 7. No other documents are required.

N/A

c. Study duration and number of study visits required of research participants.

Participants will be in this trial for up to 20 weeks including screening and follow-up.

d. Blinding, including justification for blinding or not blinding the trial, if applicable.

This study will not be blinded. All participants will receive study drug therefore blinding is not applicable.

e. Justification of why participants will not receive routine care or will have current therapy stopped.

Participants will need to stop current therapy in order to qualify for the study. In order to clearly elucidate the efficacy of abrocitinib against PN and CPUO, it is important for concurrent therapies to be halted. It is also important to note that the majority of therapies offered to these patients have poor efficacy in controlling PN and CPUO.

Participants will continue to receive other routine care.

f. Justification for inclusion of a placebo or non-treatment group.

There is no placebo group in this study. As this is an early phase, small study, we will not include a placebo group. If the data is suggestive of efficacy, a full blinded, and placebo-controlled study will be done.

g. Definition of treatment failure or participant removal criteria.

Approval Date: 3/16/2022
Principal Investigator: [name]
Application Number: IRB00262268

Discontinuation Criteria

Discontinuation from Study Treatment

Temporary Interruption of Investigational Product

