In some circumstances, patients may need to temporarily interrupt treatment as a result of AEs or abnormal laboratory values that may have an unclear relationship to investigational product.

For the abnormal laboratory findings and clinical events (regardless of relatedness) listed in [Table 1](#), specific guidance is provided for temporarily interrupting treatment and when treatment may be restarted. Retest frequency and timing of follow-up laboratory tests to monitor the abnormal finding is at the discretion of the investigator. Investigational product that was temporarily interrupted because of an AE or abnormal laboratory value not specifically covered in [Table 1](#) may be restarted at the discretion of the investigator.

Laboratory Measure	Action	Monitoring Guidance
Lipid parameters	Patients should be managed according to international clinical guidelines for hyperlipidemia	12 weeks after initiation of treatment and thereafter according to international clinical guidelines for hyperlipidemia
Absolute Neutrophil Count (ANC)	Treatment should be interrupted if ANC < 2×10^9 cells/L and may be restarted once ANC return above this value	
Absolute Lymphocyte Count (ALC)	Treatment should be interrupted if ALC < 0.5×10^9 cells/L and may be restarted once ALC return above this value	
Hemoglobin (Hb)	Treatment should be interrupted if Hb < 11 g/dL and may be restarted once Hb return above this value	Before treatment initiation (see exclusion criteria too) and thereafter according to routine patient management
Hepatic transaminases	Treatment should be temporarily interrupted if drug-induced liver injury is suspected	

[Table 1](#) Criteria for Temporary Interruption of Investigational Product

Hold Investigational Product if the Following Laboratory Test Results or Clinical Events Occur:	Investigational Product May be Resumed When:
Symptomatic herpes zoster	All skin lesions have crusted and are resolving
Infection that, in the opinion of the investigator, merits the IP being interrupted.	Resolution of infection that, in the opinion of the investigator, merits the IP being restarted.

Abbreviations: ALT = alanine aminotransferase; AST = aspartate aminotransferase; IP = investigational product; ULN = upper limit of normal.

Approval Date: 3/16/2022
Principal Investigator: [name]
Application Number: IRB00262268

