1.1.2. Permanent Discontinuation from Investigational Product

Investigational product must be permanently discontinued if the patient or the patient's designee requests to discontinue investigational product.

Discontinuation of the investigational product for abnormal liver tests should be considered by the investigator when a patient meets 1 of the following conditions:

- ALT or AST $>2.5 \times$ ULN
- ALT or AST $>2 \times$ ULN with the appearance of fatigue, nausea, vomiting, right upper-quadrant pain or tenderness, fever, rash, and/or eosinophilia ($>5\%$)
- ALP $>3 \times$ ULN that is deemed to be of liver origin and drug-related
- ALP $>2.5 \times$ ULN with the appearance of fatigue, nausea, vomiting, right upper-quadrant pain or tenderness, fever, rash, and/or eosinophilia ($>5\%$)

Investigational product should be permanently discontinued if any of the following laboratory abnormalities are observed:

- White blood cell count $<1000 \text{ cells}/\mu\text{L}$ ($1.00 \times 10^3/\mu\text{L}$ or $1.00 \text{ billion}/\text{L}$)
- ANC $<1000 \text{ cells}/\mu\text{L}$ ($1.00 \times 10^3/\mu\text{L}$ or $1.00 \text{ billion}/\text{L}$)
- Lymphocyte count $<500 \text{ cells}/\mu\text{L}$ ($0.50 \times 10^3/\mu\text{L}$ or $0.50 \text{ billion}/\text{L}$)
- Hemoglobin $<10.0 \text{ g/dL}$; ($<100.0 \text{ g/L}$)
- Platelet count $<75,000/\text{mm}^3$; ($<75.0 \times 10^9/\text{L}$)
- Creatinine (serum) $>1.5 \times$ ULN
- Total bilirubin $>1.5 \times$ ULN
- Diastolic: recurrent or persistent (≥ 24 hours) of symptomatic increase from baseline in the same posture, by $>20 \text{ mmHg}$

Note: Temporary interruption rules must be followed where applicable. For laboratory values that meet permanent discontinuation thresholds, investigational product should be discontinued. However, if in the opinion of the investigator the laboratory abnormality is due to intercurrent illness such as cholelithiasis or another identified factor, laboratory tests may be repeated. Only when the laboratory value meets resumption thresholds following the resolution of the intercurrent illness or other identified factor may the investigator restart investigational product after consultation with the Pfizer-designated medical monitor. In addition, patients will be discontinued from investigational product in the following circumstances:

- Pregnancy
- Malignancy
- HBV DNA detected with a value above limit of quantitation
- Development of a VTE (DVT/PE) during the study

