h. Description of what happens to participants receiving therapy when study ends or if a participant's participation in the study ends prematurely.

At the conclusion of the study, study drug will not be available to participants any longer. This drug is not yet FDA approved and no long-term extension studies are

Approval Date: 3/16/2022
Principal Investigator: [name]
Application Number: IRB00262268

planned. Participants will discuss with their physician regarding the proper course of future treatment for their condition.

- i. If biological materials are involved, please describe all the experimental procedures and analyses in which they will be used.

Translational Component

Please note that both skin tissue and blood samples will be sent to Duke University for analysis as described below. We do intend to publish with the Duke team however it's not a straight collaboration (fee for service - no subcontract). We will send them samples for the biomarker analysis. We will pay for services done there. Duke will return any unused samples so there will be no sample ownership change. Any residual specimens will be returned to [name] at JHU.

Skin biomarker analysis

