Secondary aims will be analyzed using appropriate statistical tests as outlined below, and missing data will be corrected with Multiple Imputation (MI) and we will assume that missing data is Missing at Random (MAR).

For secondary analyses, a multivariable logistic regression will be used to calculate the odds ratios of different study arms (PN and CPUO) achieving a 4-point reduction in PP-NRS and in SD NRS.

To analyze the PN-IGA, PROMIS Itch Questionnaire, PAS, 5D Pruritus Score, DLQI, HADS, and EQ-5D and detect differences between baseline through Week 12, an ordinal regression will be used because these are non-parametric, ordinal scales.

IgA for PN is not validated in the US, so we are using it as an additional secondary efficacy measure. Appendix D has a simplified version we are applying to this study. Eczema and psoriasis IgA are similarly qualitative. Analysis of PN/CPUO IgA will be an ordinal scale based on qualitative scaling determined at the site visit. We will analyze IgA with an ordinal regression, same as other scales mentioned above.

Atopy will be defined as a binary variable where patients have 2 out of 3: underlying history of atopic dermatitis, history of seasonal allergies, or asthma.

Among PN patients taking 200 mg of abrocitinib, we will use a linear regression to compare PP-NRS reduction from baseline with week 12, among PN patients with atopy and PN patients without atopy.

Approval Date: 3/16/2022
Principal Investigator: [name]
Application Number: IRB00262268

d. Early stopping rules.

Patients may withdraw at any time or they will be asked to end participation if the physician determines that discontinuation is in the patient's best interest. Data collected may be used if any endpoints are reached.

8. Risks

a. Medical risks, listing all procedures, their major and minor risks and expected frequency.

Foreseeable and known risks of study drug

There is a risk that participants might experience discomfort or side effects with the use of the study drug or procedures. Some of them are still unknown at this stage. In some cases, **side effects can be serious, long-lasting, permanent, or life-threatening**. The study doctor is trained to take the appropriate measures to reduce risks and limit any discomforts you may experience.

Side Effects:

- The most commonly reported side effects are:
 - Nausea (1 in 7 people)
 - Nasopharyngitis (1 in 8 people)
 - Headache (1 in 25 people)
- Rare but serious side effects include:

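### The plan does not separate stopping abrocitinib from leaving the study, so patients who stop early can lose the Week 12 primary score and the Week 16 adverse event visit

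*Combined protocol and SAP*

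**What the plan says.** - **Section 7d, Early stopping rules.** Patients may withdraw, or "they will be asked to end participation if the physician determines that discontinuation" serves them best. The sentence does not say whether discontinuation means of drug or of study, and it refers to none of the triggers in 4g. The next sentence makes use of the collected data conditional on an endpoint having been reached, without saying which.
- **Section 4g.** The prompt is "Definition of treatment failure or participant removal criteria". The answer consists of rules for the product. On interruption, "patients may need to temporarily interrupt treatment as a result of AEs or abnormal laboratory values", with retest timing left to the investigator. Under 1.1.2, "Investigational product should be permanently discontinued if any of the following laboratory abnormalities are observed". For pregnancy, malignancy, quantifiable HBV DNA and venous thromboembolism, "patients will be discontinued from investigational product in the following circumstances". If a laboratory abnormality has another identified cause and the value has recovered to the resumption threshold, only then "may the investigator restart investigational product after consultation with the Pfizer-designated medical monitor".
- **Section 4h.** The prompt covers both normal completion and premature end. The answer is that drug will no longer be supplied, that no extension is planned, and that "Participants will discuss with their physician regarding the proper course of future treatment for their condition".
- **Section 4a, text and schedule table.** Treatment runs 12 weeks, to Visit 6. PP-NRS and adverse event monitoring are marked at Visits 2 to 7. There is no early-termination visit and no visit timed from the last dose. Safety laboratory tests are marked at Visits 1 to 6 but not at Visit 7, while the text for Visits 2 to 7 has blood taken every time.
- **Sections 7a and 7c.** The primary outcome is percent PP-NRS reduction from baseline to Week 12. Least-squares means are to deal with missing data for it. Secondary aims use multiple imputation under missing at random.

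**The concern.** A site that has just stopped a patient's drug needs to know whether the patient still comes to visits. Section 4g speaks only of the product, section 7d speaks of ending participation, and section 4h, where the answer belongs, does not give it. One site may keep such a patient in follow-up and another may not, and both would be following the text.

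Two things are at stake. Safety and tolerability is a secondary objective (section 2) in a trial with no placebo group (section 4f), so what happens after a stopping event is part of what the trial is meant to learn. The primary endpoint also needs a Week 12 score. If that score is absent because the drug was not tolerated, its absence is related to treatment, and the remaining patients are a selected group.

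**Working it through.** The documents state no sample size, dropout rate or discontinuation rate, so there is no planned figure to reproduce. The check has three parts.

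**1. The passages side by side.** Section 4g stops or interrupts the product and never says that the patient leaves. Its restart provision presupposes that the patient is still being observed. Section 7d asks a patient to leave when the physician judges discontinuation to be best. A patient stopped under 4g can fall under both: still observed with a view to restart, or asked to leave. Section 4h does not settle it. The passages must be reconciled.

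**2. What is lost if 7d is applied at the time drug stops.** Inputs are the visit weeks in the section 4a schedule: Visit 3 = Week 2, Visit 4 = Week 4, Visit 5 = Week 8, Visit 6 = Week 12, Visit 7 = Week 16. Weeks lost = 16 minus the week of stopping.

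| Drug stopped at | Visits missed | Weeks lost | Marked safety laboratory sets missed | Week 12 PP-NRS | Week 16 visit |
|---|---|---|---|---|---|
| Visit 3, Week 2 | 4 (Visits 4 to 7) | 16 - 2 = 14 | 3 (Visits 4, 5, 6) | lost | lost |
| Visit 4, Week 4 | 3 (Visits 5 to 7) | 16 - 4 = 12 | 2 (Visits 5, 6) | lost | lost |
| Visit 5, Week 8 | 2 (Visits 6, 7) | 16 - 8 = 8 | 1 (Visit 6) | lost | lost |

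Completers have 16 - 12 = 4 weeks of scheduled off-drug follow-up, ending in a visit with adverse event monitoring, vital signs and PP-NRS. A patient stopped at or after Visit 6 keeps the Week 12 score.

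**3. Effect on the primary mean, as an illustration only.** Let d be the fraction lost, and let the gap be the retained patients' mean percent reduction minus the mean that the lost patients would have had at Week 12. The mean over everyone is (1 - d) x retained mean + d x lost mean. A retained-only mean therefore exceeds it by d x gap. Both inputs are assumptions; neither is in the documents.

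| d (assumed) | Gap 20 points | Gap 40 points | Gap 60 points |
|---|---|---|---|
| 5% | 1 | 2 | 3 |
| 10% | 2 | 4 | 6 |
| 20% | 4 | 8 | 12 |

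If the gap is zero there is no bias, and if it is negative the direction reverses. The table describes a mean over retained patients only. An analysis that uses a patient's earlier scores could do better, but section 7c describes a two-way model by diagnosis and week and mentions no patient-level term that would link those scores to the missing one.

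**The case against.** The strongest reply is that the documents contain no rule removing everyone who stops drug for safety. A reader might infer one from 7d together with the 4g prompt, but the text does not support it. The prompt is the application form's wording. The answer beneath it stops only the product, and 7d rests on the physician's judgement and cites no 4g trigger. Interrupted patients may restart, and so may some with permanent-stop laboratory values. Follow-up laboratory tests are foreseen for interruptions, though at the investigator's discretion and on no schedule. All of this stands. It makes the defect an unresolved ambiguity with a missing follow-up provision.

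The contrast with completers is also narrower than it may appear. As extracted, the schedule marks neither safety laboratory tests nor HBV DNA at Visit 7, so on the table completers' off-drug visit would not show recovery of a laboratory value either. The firm contrast is adverse event monitoring, vital signs and PP-NRS.

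A reader might further infer that no analysis could recover the lost scores. That goes too far. If missingness depends on recorded tolerability or laboratory data, an analysis conditioning on those data can be valid under missing at random. What can be said is that the plan does not specify such an analysis for the primary endpoint and does not name these variables for the imputation.

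Finally, an off-drug Week 12 score is not self-evidently the value wanted. It may reflect other therapy, since participants had to stop their previous treatment to enter (section 4e). That is a reason to define its use, and it can only be used if it is collected.

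**Conclusion.** The point holds as an ambiguity with consequences. Sections 4g, 4h and 7d do not say whether stopping drug ends participation, and no passage secures a Week 12 score or an off-drug safety contact for those who stop. Applied as written, 7d costs a patient stopped at Week 2, 4 or 8 a total of 4, 3 or 2 visits, with the primary endpoint and the Week 16 adverse event visit among them each time.

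These counts assume that participation ends at the visit where drug is stopped and that the schedule was extracted correctly. How many patients would be affected, and how large any bias would be, cannot be determined from the documents. The 1 to 12 point range rests wholly on assumed inputs. The change should be made: it is cheap, and data that were not collected cannot be obtained later.

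**What to change.** - **Reconcile 4g, 4h and 7d** so that stopping drug does not by itself end data collection.
- **Follow-up.** Invite participants who stop drug and remain willing to the already-scheduled non-invasive assessments: at least the Week 12 PP-NRS and adverse event monitoring, including the off-drug visit. Leave biopsy and clinical care to the investigator.
- **Analysis.** Flag Week 12 scores obtained off drug and state in 7c how they enter the primary analysis. Let this replace the sentence in 7d that makes use of collected data depend on an unspecified endpoint.
- **Schedule.** Reconcile the unmarked Visit 7 safety laboratory cell with the text that has blood taken at every visit.

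No stopping threshold or clinical rule is proposed here.

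The cost is protocol wording and a few visits after drug is stopped. Some participants will decline them, and some Week 12 scores will reflect off-drug status or other therapy.
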